6.2 Investigational Products

6.2.1 Amgen Investigational Product: Carfilzomib

Carfilzomib will be provided by Amgen Inc.

Carfilzomib is supplied as a sterile, lyophilized, white to off-white powder, ready for reconstitution. It is supplied for single use in 50 mL Type 1 glass vials containing 60 mg of carfilzomib drug product with an elastomeric stopper and flip-off lid. Upon reconstitution with [REDACTED] mL of preservative-free sterile water for injection (sWFI), the reconstituted solution contains 2 mg/mL carfilzomib, [REDACTED] mg/mL sulfobutylether beta-cyclodextrin sodium (SBECD), and [REDACTED] mg/mL citrate buffer, at pH [REDACTED] to [REDACTED].

Carfilzomib is supplied in labelled cartons containing 4 single use vials per carton.

Carfilzomib must be stored between [REDACTED] °C to [REDACTED] °C and remain protected from light.

6.2.1.1 Carfilzomib: Dosage, Administration, and Schedule

Carfilzomib will be administered as an IV infusion. On days when more than 1 investigational product is administered, the required order of administration is as follows: dexamethasone, pre-infusion medications for daratumumab, carfilzomib, daratumumab, and post-infusion medications for daratumumab. Subjects in arm 1 do not require prehydration, however, prehydration can be administered at investigator's

discretion on cycle 1 day 9 and cycle 1 day 16. Mechanical infusion pumps are recommended, but gravity-dependent infusions are permitted if the 30-minute infusion duration can be reliably maintained. For patients with baseline chronic hepatic impairment (mild, moderate), reduce the starting and subsequent doses of carfilzomib by 25% (ie, 15 mg/m² day 1 and 2 of cycle 1 and 42 mg/m² day 8 cycle 1 and thereafter). In case of resolution of hepatic abnormalities, dose escalation may be considered.

Carfilzomib will be dosed twice weekly over 30 ± 5 minutes, on days 1, 2, 8, 9, 15, and 16 of each 28-day cycle. The administration may be within ± 2 days for each scheduled dose. The dose will be 20 mg/m² on cycle 1 days 1 and 2 and 56 mg/m² beginning on cycle 1 day 8 and thereafter. See [Table 13](#) and [Table 14](#) to review the arm 1 and arm 2 dosing schedules, respectively.

Each subject's first dose of carfilzomib will be calculated based upon baseline body surface area (BSA) using the Mosteller formula. In subjects with BSA of greater than 2.2 m², the dose should be capped based on a BSA of 2.2 m². The dose for each subject should not be revised unless the subject experiences a change in body weight of > 20% in which case the BSA and dose should be recalculated. The dose can also be modified in response to toxicity following the dose modification guideline tables.

The planned dose (mg/m²), dose (mg), start date/time, stop date/time, reason for change in planned dose, reason for dose change/withheld, reason for dose delay, reason for dose interruption and package lot number of carfilzomib is to be recorded on each subject's electronic case report form (eCRF).

6.2.1.1.1 Intravenous Prehydration

Subjects in arm 2 will receive IV prehydration prior to each carfilzomib infusion during cycle 1. For subjects in arm 1, no prehydration for carfilzomib will be required on days of daratumumab administration.

Prehydration will consist of 250 mL normal saline or other appropriate IV fluid.

Thereafter, carfilzomib prehydration should only be administered if the subject's condition and/or risk factors require it. The total volume of prehydration and the reason for prehydration after cycle 1 will be recorded.

6.2.1.2 Carfilzomib: Dosage Adjustments, Delays, Rules for Withholding or Restarting, Permanent Discontinuation

Carfilzomib may be discontinued, temporarily delayed, or dosage temporarily reduced, in the event of a treatment-related toxicity that, in the opinion of the investigator, warrants

the discontinuation, temporary delay or dose reduction, as indicated in [Table 3](#) and [Table 4](#). The subject will be considered on protocol treatment while receiving either carfilzomib or daratumumab (ie, if either carfilzomib or daratumumab are discontinued or interrupted, the subject is still considered on treatment if still taking the other investigational product).

If day 1 of a cycle is delayed, all subsequent doses within the cycle and also day 1 of subsequent cycles should be adjusted accordingly to maintain the 28-day cycle duration. However, if a within-cycle dose is delayed, then the dates of the subsequent within-cycle doses should not be adjusted. For within-cycle doses, if administration does not commence within the allowable window of the scheduled administration date, then the dose will be considered a missed dose. Administration may resume at the next planned dosing date. A missed dose will not be made up.

Carfilzomib must be discontinued permanently if a delay of more than 6 weeks is required due to unresolved toxicity.

6.2.1.3 Carfilzomib: Dose Reduction Levels

Dose reduction levels of carfilzomib for toxicity management of individual subjects are provided in [Table 2](#). Subjects that require a dose level reduction and tolerate the reduced dose for 1 full cycle, may at the discretion of the treating physician increase the dose to a prior dose starting with the next cycle except when the dose reduction is due to: pulmonary hypertension, pulmonary toxicity, grade 3 or worse cardiac failure, and drug-induced hepatotoxicity.

Table 2. Dose Decrements for Carfilzomib

Dose ^{a, b} (mg/m ²)	First Dose Reduction Dose -1 (mg/m ²)	Second Dose Reduction Dose -2 (mg/m ²)	Third Dose Reduction Dose -3 (mg/m ²)	Fourth Dose Reduction Dose -4 (mg/m ²)
56	45	36	27	20

CxDx = cycle X day X

^a If dose reduction of carfilzomib is required on C1D1 or C1D2, the investigator should contact the medical monitor to discuss the situation, before any additional doses of carfilzomib are administered.

^b For patients with baseline chronic hepatic impairment (mild, moderate), reduce the starting and subsequent doses of carfilzomib by 25% (ie, 15 mg/m² day 1 and 2 of cycle 1 and 42 mg/m² day 8 cycle 1 and thereafter).

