4.1 Inclusion Criteria

- 101 Relapsed or progressive multiple myeloma after last treatment
- 102 Males or females ≥ 18 years of age
- 103 Measurable disease with at least 1 of the following assessed within 21 days prior to randomization:
 - IgG multiple myeloma: serum monoclonal paraprotein (M-protein) level ≥ 1.0 g/dL,
 - IgA, IgD, IgE multiple myeloma: serum M-protein level ≥ 0.5 g/dL,
 - urine M-protein ≥ 200 mg/24 hours,
 - in subjects without measurable serum or urine M-protein, serum free light chain (SFLC) ≥ 100 mg/L (involved light chain) and an abnormal serum kappa lambda ratio
- 104 Eastern Cooperative Oncology Group (ECOG) Performance Status (PS) of 0 to 2 (see Appendix D)
- 105 Patients must have at least PR to at least 1 line of prior therapy

-
- 106 Received at least 1 but not more than 3 prior lines of therapy for multiple myeloma (induction therapy followed by stem cell transplant and consolidation/maintenance therapy will be considered as 1 line of therapy, see [Appendix E](#) for guidance)
- 107 Prior therapy with carfilzomib is allowed as long as the patient had at least a PR to most recent therapy with carfilzomib, was not removed due to toxicity, did not relapse within 60 days from discontinuation of carfilzomib, and will have at least a 6-month carfilzomib treatment-free interval from last dose received until first study treatment. (Patients may receive maintenance therapy with drugs that are not proteasome inhibitors or CD38 antibodies during this 6-month carfilzomib treatment free interval)
- 108 Prior therapy with anti-CD38 antibodies is allowed as long as the patient had at least a PR to most recent therapy with CD38 antibody, was not removed due to toxicity, did not relapse within 60 days from intensive treatment (at least every other week) of CD38 antibody therapy, and will have at least a 6-month CD38 antibody treatment-free interval from last dose received until first study treatment.
- 109 Left ventricular ejection fraction $\geq 40\%$ as assessed by transthoracic echocardiogram (TTE)
- 110 Adequate hepatic function within 21 days prior to randomization:
- bilirubin < 1.5 times the upper limit of normal (ULN)
 - aspartate aminotransferase (AST) and alanine aminotransferase (ALT) < 2.5 times the ULN

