6.2.1.5 Carfilzomib: Guidelines of Nonhematologic Toxicity

Guidelines for dose modification in the event of nonhematologic toxicities are summarized in [Table 4](#).

Table 4. Dose Modification Guidelines for Nonhematologic Toxicities

Symptom/Sign/Investigation	Recommended Action
Renal Dysfunction^a:	
CrCl \geq 15 mL/min	Full dose
CrCl < 15 mL/min (NCI-CTCAE grade 4)	Hold dose and monitor renal function. If attributable to carfilzomib , resume when renal function has recovered to within 25% of baseline; restart at 1 dose level reduction. If not attributable to carfilzomib, dosing may be resumed at the discretion of the investigator. If dialysis required, use the maximal dose of 20 mg/m ² and administer carfilzomib after dialysis.
Chronic dialysis stable for \geq 30 days	Dose may be re-escalated up to full dose as clinically tolerated
Hepatic Dysfunction and Related Investigations	
Mild to moderate liver dysfunction: defined as 2 consecutive values, at least 28 days apart, of: (1) total bilirubin (> 33% direct) > 1x ULN to < 3x ULN OR (2) an elevation of AST and/or ALT with normal bilirubin	25% dose reduction. Dose may be re-escalated if liver function tests return to normal and drug-induced hepatotoxicity is excluded.
Grade 3 elevation in ALT and/or AST (> 5x ULN)	Hold carfilzomib until resolution to baseline. Monitor any abnormality weekly. Resume carfilzomib with a 25% dose reduction if drug-induced hepatotoxicity is excluded.
Grade 3 elevation in total bilirubin	Hold carfilzomib until resolution to baseline. Monitor total bilirubin and direct bilirubin weekly. Upon resolution of total bilirubin to normal, resume carfilzomib dosing with a 25% dose reduction if drug-induced hepatotoxicity is excluded.
Drug-induced hepatotoxicity (attributable to carfilzomib)	Discontinue carfilzomib
Other Nonhematologic Toxicities	
Tumor lysis syndrome: 3 or more of the following: 
 • increase in creatinine of \geq 50% from baseline • increase in uric acid of \geq 50% from baseline • increase in phosphate of \geq 50% from baseline • increase in potassium of \geq 30% from baseline • decrease in calcium from baseline OR • increase in LDH of \geq 2-fold from baseline 	Hold carfilzomib until all abnormalities in serum chemistries have resolved; resume at full dose.

Footnotes defined on the next page of the table

Table 4. Dose Modification Guidelines for Nonhematologic Toxicities

Symptom/Sign/Investigation	Recommended Action

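### Table 2 prints no carfilzomib decrement for subjects on 42 mg/m² (its first reduction, 45 mg/m², is 7.1% higher), and Table 4's grade 3 bilirubin row has two restart conditions

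*Protocol*

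**What the plan says.** **Standard dose.** Protocol section 6.2.1.1: "The dose will be 20 mg/m² on cycle 1 days 1 and 2 and 56 mg/m² beginning on cycle 1 day 8 and thereafter".

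**Hepatic start.** The same section, and footnote b to Table 2 in section 6.2.1.3, tell sites to "reduce the starting and subsequent doses of carfilzomib by 25" per cent in subjects with mild or moderate chronic hepatic impairment at baseline. The result is spelled out as "15 mg/m² day 1 and 2 of cycle 1 and 42 mg/m² day 8 cycle 1 and thereafter". Footnotes to Tables 13 and 14 repeat it. Footnote b hangs on the Dose column of Table 2, so these subjects fall within that table.

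**Ladder.** Section 6.2.1.3 opens: "Dose reduction levels of carfilzomib for toxicity management of individual subjects are provided in" Table 2. That table has one row: 56, then 45 under "First Dose Reduction Dose -1", then 36, 27 and 20 mg/m².

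**Rules that use the ladder.** Table 3 (bleeding or platelets below 10 × 10⁹/L; ANC below 0.5 × 10⁹/L) and Table 4 (among others, attributable renal dysfunction, grade 3 or higher heart failure, dyspnea, grade 3 or higher hypertension) call for one decrement or one dose level. Neither table makes an exception for subjects on 42.

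**Hepatic rows of Table 4.**
- Mild-to-moderate liver dysfunction, action: "25% dose reduction. Dose may be re-escalated if liver function tests return to normal and drug-induced hepatotoxicity is excluded". The trigger is two consecutive readings 28 or more days apart. They must show either total bilirubin above 1 and below 3 times ULN with more than 33% direct, or raised AST/ALT with normal bilirubin.
- Grade 3 total bilirubin: the row first says to hold until the value is back at baseline, then: "Upon resolution of total bilirubin to normal, resume carfilzomib dosing with a 25% dose reduction if drug-induced hepatotoxicity is excluded".

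**Eligibility.** Inclusion criterion 110 admits "bilirubin < 1.5 times the upper limit of normal (ULN"), and AST and ALT below 2.5 times ULN.

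**The concern.** A dose-modification table should give every subject it covers a lower level to move to. Table 2 brings in subjects who start at 42 mg/m² but lists levels only from 56. When such a subject has a toxicity for which Table 3 or 4 orders one decrement, the only entry with the matching label is higher than the dose that produced the toxicity. The site then has to devise its own repair. Carfilzomib exposure and the number of reductions still available would depend on the site, in subjects already judged to need a lower dose.

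The grade 3 bilirubin row raises a different problem. It gives two conditions for restarting, and for a subject who entered with mildly raised bilirubin they are not the same event. Two sites could treat identical laboratory values differently.

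The mild-to-moderate liver row names neither a comparison with baseline nor the dose from which the 25% is taken. It is therefore unclear what it asks for in a subject who already started 25% lower.

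**Working it through.** **1. Reproduce the stated hepatic doses.** Inputs: 20 and 56 mg/m² (section 6.2.1.1) and a 25% reduction (footnote b).
- 20 × 0.75 = 15.0
- 56 × 0.75 = 42.0

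Both match the protocol exactly.

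**2. Compare 42 with the Table 2 ladder** (56, 45, 36, 27, 20).
- Printed first reduction: 45 − 42 = +3 mg/m²; 45/42 = 1.071, so 7.1% higher.
- Printed levels below 42: 36, 27 and 20.
- No level is labelled as a reduction from 42.

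**3. Repairs open to a site.** These show the spread only; neither is put forward as right.

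| Reading | First step from 42 | Change | Steps available |
|---|---|---|---|
| Next printed level below 42 | 36 | 36/42 − 1 = −14.3% | 3 (36, 27, 20) |
| Every Table 2 level scaled by 0.75 | 45 × 0.75 = 33.75 | 33.75/42 − 1 = −19.6% | 4 (33.75, 27, 20.25, 15) |

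The scaled ladder is printed nowhere.

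**4. Subjects affected beyond the hepatic start.** A 25% hepatic reduction under Table 4 takes a subject from 56 to 42 during treatment, and a later one-level reduction then meets the same gap. From the other printed levels a 25% cut gives 45 → 33.75, 36 → 27, 27 → 20.25 and 20 → 15. Of these, 27 is a Table 2 level, 20.25 is close to the printed 20, and 33.75 and 15 are not on the ladder.

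**5. Grade 3 bilirubin row.** Take an eligible subject with baseline bilirubin between 1 and 1.5 times ULN.
- The hold ends when bilirubin is back at baseline, which is above ULN.
- Dosing resumes when bilirubin is normal, which is at or below ULN.

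A value that has returned to baseline meets the first condition and fails the second. For a subject with normal baseline bilirubin the two conditions need not conflict.

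**6. Mild-to-moderate row in a subject already on 42.**
- 25% taken from the current dose: 42 × 0.75 = 31.5 mg/m², which is 31.5/56 = 56.25% of 56.
- 25% taken from 56: 56 × 0.75 = 42, so no change.

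The row does not choose between them.

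**7. When that row could first apply.** Table 11 schedules chemistry on days 1, 8, 15 and 22 of cycle 1 and on day 1 from cycle 2. Consecutive scheduled on-treatment readings are therefore 7 days apart until cycle 2 day 1. The first consecutive pair 28 days apart is cycle 2 day 1 with cycle 3 day 1.

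**The case against.** The best defence is that no printed number is wrong: 45 is the first reduction from 56, which is what the row shows. A site told to reduce would not give 45 to a subject on 42, because that is not a reduction. Footnote b also speaks of subsequent doses, which could be taken to scale the whole ladder. So a reader might infer from Table 2 that doses will actually be raised after toxicity, but the documents do not support that as an expected outcome. What stands is that no step from 42 is printed. The footnote's own gloss gives only 15 and 42, so scaling remains a guess, and the two natural guesses differ in both dose and number of steps.

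A reader might also infer that a subject with stable, mildly abnormal liver tests will certainly be cut twice, and by about cycle 2. The documents do not support this.
- The row needs consecutive readings, and its bilirubin limb also needs more than 33% direct and below 3 times ULN. Not every subject admitted by criterion 110 meets these.
- The earliest scheduled on-treatment pair is completed at cycle 3 day 1.
- Section 6.2.1.2 introduces Tables 3 and 4 as actions that may be taken for treatment-related toxicity that the investigator thinks warrants them.
- The row names no reference dose.

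The ambiguity remains, because the row is not limited to drug-related change: hepatotoxicity attributed to carfilzomib has a separate row.

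A third tempting inference is that the bilirubin row will force permanent discontinuation under the 6-week rule in section 6.2.1.2. That is conjecture. The rule concerns delay for unresolved toxicity, and a bilirubin back at its pre-treatment value is arguably resolved. Nor do the documents equate a baseline bilirubin of 1 to 1.5 times ULN with the hepatic impairment that triggers the lower start.

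Finally, timing limits the benefit. The Amendment 6 rationale records that the primary endpoint has been met, so changes now help only subjects still on treatment. The same amendment allows longer treatment, so the tables remain in use.

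**Conclusion.** Two inconsistencies hold. First, Table 2 covers subjects on 42 mg/m² through footnote b but prints no decrement for them, and its first reduction is 7.1% above their dose. The same gap reaches anyone moved from 56 to 42 by Table 4. This rests only on the printed doses and on Tables 3 and 4 making no exception. Second, the grade 3 bilirubin row contains two restart conditions that diverge when baseline bilirubin is between 1 and 1.5 times ULN.

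The unstated reference dose and baseline rule in the mild-to-moderate row is a lesser point. It is an ambiguity between 31.5 and 42 mg/m², not a demonstrated double reduction.

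The documents do not say how many subjects are affected, and no effect on alpha, power or the primary comparison is shown. This is a safety and dosing-consistency point that should be corrected. It does not threaten the trial's conclusions.

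**What to change.** The sponsor's clinical team should reconcile section 6.2.1.1, Table 2 with footnote b, and the hepatic rows of Table 4, so that the protocol states:
- the decrement levels that apply to a subject on 42 mg/m², whether reached by the hepatic start or by a 25% reduction on treatment;
- for the mild-to-moderate row, the dose from which the 25% is taken, and whether the row applies to values unchanged from a baseline that already set the lower start;
- one restart condition for grade 3 bilirubin.

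The choice of levels and conditions is clinical, and none is proposed here. The cost is an added table row and short wording changes, by amendment or dosing memo, with no extra tests or subjects.

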6.2.1.4 Carfilzomib: Guidelines for Hematologic Toxicity

Guidelines for carfilzomib dose modification in the event of thrombocytopenia and neutropenia are summarized in [Table 3](#).

Table 3. Dose Modification Guidelines for Thrombocytopenia and Neutropenia

Hematologic toxicity	Recommended Action	
Thrombocytopenia		
When platelets fall to < 30 x 10 ⁹ /L and for each subsequent drop to < 30 x 10 ⁹ /L	If platelets 10 to 30 x 10 ⁹ /L without evidence of bleeding	
 • Hold • restart at previous dose when platelets > 30 x 10⁹/L
	If evidence of bleeding or platelets < 10 x 10 ⁹ /L	
 • hold • restart at 1 dose decrement when platelets > 30 x 10⁹/L
Neutropenia		
When ANC falls to < 0.75 x 10 ⁹ /L and for each subsequent drop to < 0.75 x 10 ⁹ /L	If ANC 0.5 to 0.75 x 10 ⁹ /L	
 • continue at full dose
	If ANC < 0.5 x 10 ⁹ /L	
 • hold dose • resume at 1 dose decrement when ANC ≥ 0.5 x 10⁹/L

ANC = absolute neutrophil count.

6.2.1.5 Carfilzomib: Guidelines of Nonhematologic Toxicity

Guidelines for dose modification in the event of nonhematologic toxicities are summarized in [Table 4](#).

Table 4. Dose Modification Guidelines for Nonhematologic Toxicities

Symptom/Sign/Investigation	Recommended Action
Renal Dysfunction^a:	
CrCl \geq 15 mL/min	Full dose
CrCl < 15 mL/min (NCI-CTCAE grade 4)	Hold dose and monitor renal function. If attributable to carfilzomib , resume when renal function has recovered to within 25% of baseline; restart at 1 dose level reduction. If not attributable to carfilzomib, dosing may be resumed at the discretion of the investigator. If dialysis required, use the maximal dose of 20 mg/m ² and administer carfilzomib after dialysis.
Chronic dialysis stable for \geq 30 days	Dose may be re-escalated up to full dose as clinically tolerated
Hepatic Dysfunction and Related Investigations	
Mild to moderate liver dysfunction: defined as 2 consecutive values, at least 28 days apart, of: (1) total bilirubin (> 33% direct) > 1x ULN to < 3x ULN OR (2) an elevation of AST and/or ALT with normal bilirubin	25% dose reduction. Dose may be re-escalated if liver function tests return to normal and drug-induced hepatotoxicity is excluded.
Grade 3 elevation in ALT and/or AST (> 5x ULN)	Hold carfilzomib until resolution to baseline. Monitor any abnormality weekly. Resume carfilzomib with a 25% dose reduction if drug-induced hepatotoxicity is excluded.
Grade 3 elevation in total bilirubin	Hold carfilzomib until resolution to baseline. Monitor total bilirubin and direct bilirubin weekly. Upon resolution of total bilirubin to normal, resume carfilzomib dosing with a 25% dose reduction if drug-induced hepatotoxicity is excluded.
Drug-induced hepatotoxicity (attributable to carfilzomib)	Discontinue carfilzomib
Other Nonhematologic Toxicities	
Tumor lysis syndrome: 3 or more of the following: 
 • increase in creatinine of \geq 50% from baseline • increase in uric acid of \geq 50% from baseline • increase in phosphate of \geq 50% from baseline • increase in potassium of \geq 30% from baseline • decrease in calcium from baseline OR • increase in LDH of \geq 2-fold from baseline 	Hold carfilzomib until all abnormalities in serum chemistries have resolved; resume at full dose.

Footnotes defined on the next page of the table

Table 4. Dose Modification Guidelines for Nonhematologic Toxicities

Symptom/Sign/Investigation	Recommended Action
Congestive heart failure	Any subject with congestive heart failure, whether or not drug related, must have the dose held until resolution or return to baseline. Appropriate medical management should be initiated. If no resolution after 4 weeks, carfilzomib will be permanently discontinued.
< Grade 3	Once congestive heart failure resolves or returns to baseline, resume at full dose.
Grade ≥ 3	Once congestive heart failure resolves or returns to baseline, treatment may continue at 1 dose level reduction.
Infection (grade 3 or 4)	Hold carfilzomib. Once infection is controlled and the subject is without infection-related symptoms, and if ANC > 1.0 x 10 ⁹ /L, resume at full dose. If ANC < 1.0 x 10 ⁹ /L, follow hematologic toxicities dose reduction guidelines.
Hepatitis B Virus Reactivation	Hold carfilzomib until infection is adequately controlled (see Section 6.7.1).
Neuropathy (grade 2 with emergent pain, or grade 3)	Hold carfilzomib until resolved to ≤ grade 2 without pain; then resume at 1 dose decrement.
Neuropathy (grade 4)	Permanently discontinue carfilzomib.
Dyspnea (grade ≥ 2)	Hold carfilzomib until resolution to grade 1 or baseline, then resume at 1 dose decrement. Investigate cause and record findings. If caused by another adverse event listed in this table, follow recommendations for that adverse event.
Hypertension (SBP > 140 and/or DBP > 90, measured per Appendix F)	
< Grade 3	Continue at same dose if initiation of appropriate treatment controls hypertension (see Appendix F for guidance)
Grade ≥ 3	Hold carfilzomib until resolution to normal or baseline. Initiate appropriate anti-hypertensive therapy prior to resuming carfilzomib at 1 dose decrement.
Pulmonary toxicity: Non-infectious interstitial lung disease, acute respiratory failure, ARDS (≥ grade 3)	Hold carfilzomib until resolution to grade 1 or baseline and restart at 1 dose decrement.
Pulmonary hypertension (grade ≥ 3)	Hold carfilzomib until resolution to grade 1 or baseline and restart at 1 dose decrement
Posterior reversible encephalopathy syndrome: Headaches, altered mental status, seizures, visual loss, and hypertension	If PRES is suspected, hold carfilzomib. Consider evaluation with neuroradiological imaging, specifically MRI, for onset of visual or neurological symptoms suggestive of PRES. If PRES is confirmed, permanently discontinue carfilzomib. If the diagnosis of PRES is excluded, carfilzomib administration may resume at same dose, if clinically appropriate.

Footnotes defined on the next page of the table

Table 4. Dose Modification Guidelines for Nonhematologic Toxicities

Symptom/Sign/Investigation	Recommended Action
Progressive Multifocal Leukoencephalopathy	Patients should be monitored for any new or worsening neurologic, cognitive, or behavioral signs or symptoms that may be suggestive of PML as part of the differential diagnosis of CNS disorders. If PML is suspected, withhold administration of carfilzomib; patients should be promptly referred to a specialist and appropriate diagnostic testing should be initiated. Discontinue carfilzomib if PML diagnosis is confirmed. If the diagnosis is excluded, carfilzomib can be restarted at the same dose.
Thrombotic microangiopathy: Fever, microangiopathic hemolytic anemia, renal failure, thrombocytopenia, neurological manifestations	If the diagnosis is suspected, hold carfilzomib and manage per standard of care including plasma exchange as clinically appropriate. If TMA is confirmed, permanently discontinue carfilzomib. If the diagnosis is excluded, carfilzomib can be restarted at the same dose .
Venous thrombosis (≥ grade 3)	Hold carfilzomib and adjust anticoagulation regimen; resume at full dose once anticoagulation has been optimized per treating investigator's discretion.
Any other drug-related nonhematologic toxicity ≥ grade 3 ^b	For carfilzomib attribution, hold dose. Resume at 1 dose decrement when toxicity has resolved to grade 1 or less or to baseline grade.

Page 3 of 3

ALT = alanine aminotransferase; ANC = absolute neutrophil count; ARDS = acute respiratory distress syndrome; AST = aspartate aminotransferase; **CNS = central nervous system**; CrCl = creatinine clearance; DBP = diastolic blood pressure; LDH = lactate dehydrogenase; MRI = magnetic resonance imaging; NCI-CTCAE = National Cancer Institute-Common Terminology Criteria for Adverse Events; **PML = Progressive Multifocal Leukoencephalopathy**; PRES = Posterior Reversible Encephalopathy Syndrome; SBP = systolic blood pressure; TMA = thrombotic microangiopathy; ULN = upper limit of normal.

^a For a rapid fall from baseline in CrCl or an absolute fall of ≥ 60 mL/min, contact the medical monitor.

^b In the event of a possible drug-related nonhematologic toxicity, the investigator should, to the best of his/her ability, assess its relationship to daratumumab (D), carfilzomib (K), dexamethasone (d), or the combination of KdD to the extent possible. If both carfilzomib and daratumumab are considered likely to be involved, then recommended actions for both should be instituted.

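### For a grade 3 bilirubin rise, Protocol Table 4 ends the carfilzomib hold at baseline but resumes dosing at normal; the two differ for subjects who enter above normal

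*Protocol*

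**What the plan says.** The Table 4 row for a grade 3 rise in total bilirubin (Protocol section 6.2.1.5) reads: "Hold carfilzomib until resolution to baseline. Monitor total bilirubin and direct bilirubin weekly. Upon resolution of total bilirubin to normal, resume carfilzomib dosing". The rest of that sentence makes resumption conditional on a 25% lower dose and on drug-induced liver injury having been ruled out. The next row has carfilzomib stopped if the liver injury is attributed to it.

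Other rows of the same table handle the endpoint differently:

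- Grade 3 ALT or AST uses baseline alone: "Hold carfilzomib until resolution to baseline. Monitor any abnormality weekly. Resume carfilzomib with a 25% dose reduction".
- Hypertension of grade 3 or higher writes the two endpoints as alternatives: "Hold carfilzomib until resolution to normal or baseline".

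Three other places bear on the row:

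- Section 4.1, inclusion 110, sets an upper limit of 1.5 × ULN (not inclusive) for bilirubin, assessed within 21 days before randomization.
- Section 6.2.1.2 states: "Carfilzomib must be discontinued permanently if a delay of more than 6 weeks is required due to unresolved toxicity".
- Section 6.6, on stopping and rechallenge for hepatotoxicity, sends the reader back to Table 4 for carfilzomib and adds no criterion of its own for this case.

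**The concern.** One cell gives two endpoints for one decision. The first sentence says how long to hold, and ends the hold at *baseline*. The third says when to resume, and sets that at *normal*. For a subject whose baseline is above normal these are different values, and the eligibility criteria admit such subjects.

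At stake is consistent application of a safety instruction. With the same laboratory values, one site could restart carfilzomib and another could keep it on hold. A prolonged hold brings the 6-week rule into view. Carfilzomib is given in both arms, and SAP section 9.6.7 tabulates exposure and dose modifications with their reasons, so different readings between sites would also enter those summaries. The consequence of stopping differs by arm: under section 6.2.1.2 an arm 1 subject remains on protocol treatment while daratumumab continues, whereas arm 2 has no other investigational product.

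**Working it through.** The plan gives no figure to reproduce here. The check compares thresholds.

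**Inputs**, in multiples of ULN, with b the baseline and v the current total bilirubin:

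- Hold ends when v ≤ b (Table 4, first sentence of the row).
- Resumption is allowed when v ≤ 1.0 (Table 4, third sentence).
- Entry requires a screening value below 1.5 (inclusion 110, taken here to mean total bilirubin).
- Grade 3 is above 3 and up to 10; grade 1 is above 1 and up to 1.5 (SAP Table 5).

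**Step 1: abnormal baseline, 1.0 < b < 1.5.** Take b = 1.3.

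| v | Hold ended (v ≤ 1.3)? | Resumption allowed (v ≤ 1.0)? |
|---|---|---|
| 1.4 | no | no |
| 1.2 | yes | no |
| 0.9 | yes | yes |

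The sentences disagree wherever 1.0 < v ≤ b. The band has width b − 1.0, which is under 0.5 × ULN if the baseline value itself respects the entry limit.

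**Step 2: normal baseline.** Read literally, the mismatch can also run the other way. With b = 0.6 and v = 0.9, resumption is allowed (0.9 ≤ 1.0) but the hold has not ended (0.9 > 0.6). This disappears if *baseline* means baseline grade, because SAP Appendix C assigns grade 0 to any value that meets no grading criterion. The abnormal-baseline conflict does not disappear on that reading: the baseline is then grade 1, and the band becomes 1.0 < v ≤ 1.5. The conflict in Step 1 therefore survives both readings.

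**Step 3: what follows.** A subject falling from above 3 × ULN through the band to normal sees at most a difference in timing between the two readings. A subject who settles inside the band can restart under the first sentence and stays on hold under the third. If that hold exceeds 6 weeks, section 6.2.1.2 requires discontinuation only if the delay is due to unresolved toxicity. The protocol does not say whether a return to the subject's own pre-treatment value counts as unresolved.

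**Step 4: number affected.** The expected count is

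N × P(b > 1.0) × P(later grade 3 rise | b > 1.0) × P(drug cause excluded and v settles in the band | both).

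The documents give N = 450 and none of the three probabilities, so no count can be derived.

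**The case against.** The strongest reply is that the row is sequential: one sentence governs the hold, the other the restart, and both must be satisfied. That gives a single restart point. The reading is possible, but the row does not state it, and under it *baseline* has no function for a subject whose baseline is above normal. Where Table 4 intends alternatives, as in the hypertension row, it says so.

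A second reply is that the table offers recommended actions under a guidelines heading, and section 6.2.1.2 leaves delay, reduction and discontinuation to the investigator's opinion. That softens the effect, but an investigator following the row still meets two endpoints.

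A third is that the reduced dosing in section 6.2.1.1 for mild or moderate hepatic impairment at baseline does not prove that raised bilirubin at entry is expected. This stands: Table 4's own definition of mild to moderate liver dysfunction includes raised transaminases with normal bilirubin. The point therefore rests on inclusion 110, which shows that an above-normal baseline is permitted and says nothing about how often it occurs.

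A reader might also infer that one of the two readings leads to permanent discontinuation. The documents do not support that as a certain outcome. The 6-week rule depends on the toxicity being unresolved, and bilirubin back at its pre-treatment level is arguably resolved.

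**Conclusion.** The inconsistency is real and no other section resolves it. It is minor. It affects only subjects with a baseline above ULN who later have a grade 3 rise, have a drug cause excluded, and reach a value above ULN but no higher than baseline. Permanent discontinuation is a possible consequence, not a stated one.

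A reader might try to size it by assuming that 2% to 5% of the 450 subjects enter above ULN, which gives 9 to 23 (0.02 × 450 = 9; 0.05 × 450 = 22.5). The documents do not support that as a count of affected subjects. The percentages have no source in them, and the product counts everyone with a raised baseline before any grade 3 event. With a further assumption, equally unsourced, that 1% to 5% of those subjects have a grade 3 rise, the range falls to about 0.1 to 1.1 (9 × 0.01 = 0.09; 22.5 × 0.05 = 1.125), before drug-induced cases are removed. These figures only illustrate that the number is likely to be small.

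Nor should a reader infer a threat to the primary PFS result. That analysis uses all randomized subjects as randomized, and section 3.1 has disease assessment continue to progression despite treatment discontinuation. The Amendment 6 rationale also records that the primary endpoint had already been met.

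**What to change.** Reconcile the two sentences in the Table 4 bilirubin row so that a single restart criterion applies to every subject, including those whose baseline is above normal. State whether *baseline* means the value or the grade. Check the result against the 6-week rule in section 6.2.1.2, so that it is clear whether a subject held only because of an abnormal baseline counts as having unresolved toxicity. The choice of criterion belongs to the clinical team; this review takes no view on it.

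The cost is one table cell in the next amendment, or a clarification letter to sites. No change to the statistical analysis is needed.
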